12.4.2 Follow-up (patients taken off treatment for reasons other than POD)

Subjects who discontinue study treatment for a reason other than disease progression (including patients who achieve stable disease control at 2 years) will move into the follow-up phase and will be assessed every 12 weeks by radiologic imaging to monitor disease status.

For patients who achieved stable disease at 2 years, re-treatment on study may be allowed at the time of disease recurrence or progression with permission of the study PI.

Every effort should be made to collect information regarding disease status until the start of new anti-neoplastic therapy, disease progression, death, and end of the study.

12.4.3 Survival Follow-up

Once a subject has confirmed disease progression or starts a new anticancer therapy, the subject moves into the survival follow-up phase and should be contacted by telephone, email, or visit every 12 weeks (+/- 2 weeks) to assess survival status. Clinical notes for patients currently being treated at Columbia University Medical Center (or collaborating medical center) will also suffice

as follow up. Overall survival will be followed until death, withdrawal of consent, or the end of the study, whichever occurs first.

12.5 Unscheduled Visits

Unscheduled study visits may occur at any time if medically warranted. Any assessments performed at those visits should be recorded in the eCRF.

13. STUDY CALENDAR

Baseline evaluations are to be conducted within 1 week prior to start of protocol therapy. Scans and x-rays must be done \leq 4 weeks prior to the start of therapy. In the event that the patient's condition is deteriorating, laboratory evaluations should be repeated within 48 hours prior to initiation of the next cycle of therapy.

13.1 Safety Lead-In Calendar:

| | Screening | C1D1 | C1D15 +/- 3d | C2D1 +/- 3d |
|---|-----------|------|-----------------|----------------|
| Ruxolitinib (daily) | | X | X | X |
| Informed consent | X | | | |
| Demographics | X | | | |
| Medical history | X | | | |
| Concurrent meds | X | X | X | X |
| Physical exam | X | X | X | X |
| Vital signs | X | X | X | X |
| Height | X | X | | |
| Weight | X | X | X | X |
| Performance status | X | X | X | X |
| CBC w/diff, plts | X | X | X | X |
| Serum chemistry ^a | X | X | X | X |
| Serum Liver Function Tests ^b | X | X | X | X |
| EKG (as indicated) | X | | | |
| Adverse event evaluation | | X | X | X |
| Tumor measurements | X | | | |
| Radiologic evaluation | X | | | |
| Serum B-HCG ^c | X | | | |
| Tumor Biopsy (10 patients) | | X | | X |
| Research blood collection | | X | | X |
| Survival Follow-up | | | | X |

a: Albumin, alkaline phosphatase, total bilirubin, bicarbonate, BUN, calcium, chloride,

Columbia University Medical Center
Herbert Irving Comprehensive Cancer Center
Version Date: 27 Jul 2023

creatinine, glucose, LDH, phosphorus, potassium, total protein, SGOT [AST], SGPT [ALT], sodium

b: Albumin, alkaline phosphatase, total bilirubin, AST, ALT

c: Perform only in women of child-bearing potential

13.2 Study Calendar

| | Screening | C1D1 | C1D15 +/- 3d | C2D1 +/- 3d | C3D1 ± 3d (and D1 ± 3d of every subsequent cycles) | End of Treatment (Within 30d of last treatment) | Survival follow- up |
|---|-----------------|------|-----------------|--------------------------|--|--|---------------------------|
| Ruxolitinib | | X | | X | X | | |
| Informed consent | X | | | | | | |
| Demographics | X | | | | | | |
| Medical history | X | | | | | | |
| Concurrent meds | X | X | X | X | X | X | |
| Physical exam | X | X | X | X | X | X | |
| Vital signs | X | X | X | X | X | X | |
| Height | X | X | | | | | |
| Weight | X | X | X | X | X | X | |
| Performance status | X | X | X | X | X | X | |
| CBC w/diff, plts | X | X | X | X | X | X | |
| Serum chemistry^a | X | X | X | X | X | X | |
| Serum Liver Function Tests^b | X | X | X | X | X | X | |
| EKG (as indicated) | X | | | | | | |
| Adverse event evaluation | | X | X | X | X | X | |
| Tumor measurements | X | | | | X (every other cycle) | X | |
| Radiologic evaluation | X | | | | X (every other cycle) | X | |
| Serum B-HCG^c | X ^{b)} | | | | | | |
| Tumor Biopsy (10 patients) | X | | | X (between D1 and D8) | | | |
| Research blood collection | | X | | X | X | X | |
| Survival Follow-up | | | | | | | X |

a: Albumin, alkaline phosphatase, total bilirubin, bicarbonate, BUN, calcium, chloride, creatinine, glucose, LDH, phosphorus, potassium, total protein, SGOT [AST], SGPT [ALT], sodium

b: Albumin, alkaline phosphatase, total bilirubin, AST, ALT

c: Perform only in women of child-bearing potential

14. BIOMARKER, CORRELATIVE, AND SPECIAL STUDIES

14.1 Collection of samples for correlative studies

14.1.1 Tumor biopsy samples

Pre- and on-treatment tumor biopsies are mandatory in a minimum of 10 subjects. Subjects in whom biopsy is technically not feasible or in whom would result in unacceptable risk, in the opinion of the investigator, may be exempted from the biopsy requirement, with discussion with the principal investigator.

Timing of Biopsy Samples:

A fresh biopsy must be obtained at the following time-points:

- Prior to treatment (anytime during the screening period) (mandatory)
- On-treatment (between C2D1 and C2D8 treatment dose)) (mandatory)
- At the time of disease progression (optional)

Collection & Processing Instructions:

Collection and processing instructions are the same for all of the specified tumor biopsy time points.

A goal of at least 3 cores and up to 8 cores, if safe to obtain, will be obtained at each collection time point.

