to study medication, reversed within 5 days, and was reported as a serious adverse event (SAE). A Phase I dose escalation study and a study to evaluate food effect in Japanese healthy volunteers showed that administration of ruxolitinib with a high-fat meal led to results that were in line with results from the North American study. A Phase I dose escalation study in Chinese healthy volunteers showed similar overall results over a dose range of 10-50 mg. The pharmacokinetics of ruxolitinib was linear in the dose range studied, with a short half-life of 2-4 hours resulting in no notable drug accumulation following multiple doses.

In the repeat-dose study in healthy subjects, the intensity of an adverse event was graded according to the protocol-defined toxicity criteria based on Rheumatology Common Toxicity Criteria V 1.0. The dose-limiting AE was neutropenia, which occurred at a dose of 50 mg b.i.d. Neutropenia as an AE was noted in three subjects, all receiving the highest dose of ruxolitinib, 50 mg b.i.d. Neutropenia at the Grade 4 level, assessed as severe, led to study drug discontinuation on Day 5 in one subject, and was reported as a SAE. Neutrophil count returned to a normal level 12 days after the final dose of study medication. In two other subjects, neutropenia was Grade 1 or 2, and resolved with dose interruption or during continued dosing. The AE profile was similar for single- and multiple-dose studies, and no differences were observed between males and females. The most frequent (≥ 2 subjects) treatment-emergent AEs (TEAEs) occurring in the Phase I multiple-dose study were: neutropenia (4.2%), dizziness (2.8%), headache (2.8%) and nausea (2.8%). Overall, in healthy volunteer studies where frequent sampling of the neutrophil count was performed, a transient, reversible decrease in neutrophil count was frequently seen following dosing, which reversed after 12-24 hours off drug. Two clinical pharmacology studies are ongoing to evaluate the effect of ruxolitinib on the pharmacokinetics of orally administered midazolam in healthy males subjects and of monophasic oral contraceptives in health female subjects.

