5.3 Correlative Studies

5.3.1 Tumor biopsies for pharmacodynamic assessment

The biological activity of ruxolitinib will be assessed by performing paired tumor biopsies

at baseline, and between Cycle 2 Day 1 and Cycle 2, Day 8 of study therapy. These biopsies will be mandatory in the first 10 patients enrolled on Stage I of the study (first 18 enrolled subjects), and optional in subsequent patients. A biopsy at the time of disease progression is optional in all patients. (Note: If sufficient flash frozen tumor material is available from a prior tumor biopsy performed within 3 months of registration with no intervening therapy, then a repeat baseline biopsy will not be necessary.)

A goal of at least 3 cores and up to 8 cores from the patient's tumor biopsy specimen, if safe to obtain, will be obtained for research purposes. The first core will be placed in buffered formalin and paraffin-embedded as standard of care. Subsequent cores will be flash frozen.

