8.1.1 Investigational Agent(s)

Ruxolitinib will be administered twice daily, in the morning and evening, approximately 12 hours apart, without regard to food. If a dose is late but within 4 hours of its scheduled administration time it should be taken; if more than 4 hours have passed, the dose should be omitted and the patient should continue treatment with the next scheduled dose. If vomiting occurs while taking dose, no redosing is allowed before the next rescheduled dose.

Patients will not require any premedications, however supportive medications to control symptoms such as nausea, emesis, diarrhea, and pain will be provided for symptom control.

Doses will be self-administered. Subjects will be required to keep a pill diary (Appendix D). Each cycle of treatment will last 28 days.

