17.2 Study Endpoints and Analytic Plan

All subjects who receive at least one dose of study drug will be considered evaluable and included in the efficacy and safety analysis.

Definition of primary outcome/endpoint:

The primary endpoint is the overall response rate defined as the best response within the first 24 weeks of the start of study therapy using RECIST v. 1.1 that has been confirmed at a subsequent time point (≥ 4 weeks).

Definition of secondary outcomes/endpoints:

PFS is defined as time from enrollment to time of clinical or radiographic disease progression as defined by RECIST v.1.1 criteria. OS is defined as time from enrollment to time of death from any cause.

Analytic plan for primary objective:

The overall response rate will be summarized using point estimates and 95% confidence intervals.

Analytic plan for secondary and exploratory objectives:

- We will estimate the survival distribution for both PFS and OS endpoints using the Kaplan Meier method. The log rank test will be used to examine differences between survival curves using prognostic markers.
- For correlative studies we will apply either the Fisher's exact test or Wilcoxon Rank Sum test to examine the associations between response status and changes in markers expression for categorical and continuous variables, respectively. Because of the limited sample size, the biomarker data analysis is for exploratory research only.
- Toxicity data will be summarized by type, frequency, and severity according to the NCI CTCAE criteria v4.0.

- Pharmacokinetic and pharmacodynamic parameters will be summarized using descriptive statistics and graphical methods (individual profile plots).

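### The on-treatment pharmacodynamic biopsy is scheduled by day but not by time since dose, for a drug with a 2-4 hour half-life taken twice daily, and the two calendars disagree on the baseline biopsy

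*Combined protocol and SAP*

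**What the plan says.** **Role of the biopsies.** Section 2.2 lists pharmacodynamics as a secondary objective. Sections 3.4 and 5.3.1 assign that work to paired tumor biopsies. Section 2.3 adds an exploratory link between response and change in phosphorylated STAT3 and Cyclin D1. Section 5.1 asks for pairs from at least 10 subjects.

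**Timing of the second biopsy.** Section 14.1.1: "On-treatment (between C2D1 and C2D8 treatment dose)) (mandatory". Sections 5.1, 5.3.1, 12.2.4 and 13.2 give the same range of days. None gives a time relative to a dose.

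**Timing of the baseline biopsy.** Section 14.1.1: "Prior to treatment (anytime during the screening period) (mandatory". The main calendar (13.2) agrees: "Tumor Biopsy (10 patients) | X | | | X (between D1 and D8". The lead-in calendar (13.1) reads "Tumor Biopsy (10 patients) | | X | | X". Its columns are Screening, C1D1, C1D15 and C2D1, so Screening is blank and the first mark falls on the first dosing day.

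**The drug.** Section 4.5 reports linear kinetics "with a short half-life of 2-4 hours resulting in no notable drug accumulation following multiple doses". Section 8.1.1: "Ruxolitinib will be administered twice daily, in the morning and evening, approximately 12 hours apart, without regard to food".

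**Bloods.** Both calendars place research blood at C1D1 and C2D1, and 13.2 adds later Day 1 visits and end of treatment. No time relative to dose is given. Section 14.1.2 uses the blood for circulating immune cells and ctDNA.

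**Analysis.** Section 17.2: "Pharmacokinetic and pharmacodynamic parameters will be summarized using descriptive statistics and graphical methods (individual profile plots".

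**The concern.** When a drug clears in hours, a marker that responds to it may depend on when in the dosing interval it is sampled. Two patients with equal drug sensitivity, one biopsied soon after the morning dose and one just before the next dose, could show different pSTAT3 change for that reason alone. With about 10 pairs there is little averaging to absorb the extra variation. It could hide real target inhibition, or blur or mimic a relation with response.

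The plan does not secure what is needed to sort this out later. The shipment notices in 5.3.2 and 14.1.2 ask for the date of collection, not the clock time. The promised pharmacokinetic summary cannot help, because no concentration sample appears in 13.1, 13.2 or section 14. The biopsies are CT-guided and mandatory for these subjects, so their results should be interpretable.

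**Working it through.** **Inputs.** Half-life t½ = 2 to 4 h (section 4.5, healthy-volunteer plasma data). Dosing interval 12 h (section 8.1.1). The documents give no plasma or tumor concentration at the trial doses and no recovery time for tumor pSTAT3.

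**Step 1: check the plan's own statement.** Under first-order decay the accumulation ratio is 1/(1 − 2^(−12/t½)).
- t½ = 2 h: 1/(1 − 0.0156) = 1.016
- t½ = 4 h: 1/(1 − 0.125) = 1.143

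Both agree with the protocol's statement that accumulation is not notable.

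**Step 2: concentration swing within one interval.** Fraction of peak left after t hours = 2^(−t/t½).

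| Hours after peak | t½ = 2 h | t½ = 4 h |
|---|---|---|
| 2 | 50% | 71% |
| 4 | 25% | 50% |
| 8 | 6% | 25% |
| 12 | 1.6% | 12.5% |

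The swing is 1/0.0156 = 64-fold or 1/0.125 = 8-fold. This counts 12 h of decay from peak. If peak comes 1 h after the dose, 11 h of decay remain and the swing is 2^(11/2) = 45-fold or 2^(11/4) = 6.7-fold. The conclusion is the same.

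**Step 3: what this could mean for inhibition (illustration only).** Take inhibition = C/(C + IC50), with peak concentration *assumed* at 1, 2, 5 or 10 times IC50. The SD is that produced by sampling time alone, with times spread evenly over the stated hours after peak.

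| t½ | Peak/IC50 | Inhibition, 0-12 h | SD, 0-12 h | SD, 2-8 h | SD, 2-4 h |
|---|---|---|---|---|---|
| 2 h | 1 | 2-50% | 0.14 | 0.08 | 0.04 |
| 2 h | 2 | 3-67% | 0.19 | 0.12 | 0.05 |
| 2 h | 5 | 7-83% | 0.24 | 0.14 | 0.05 |
| 2 h | 10 | 14-91% | 0.25 | 0.13 | 0.03 |
| 4 h | 1 | 11-50% | 0.12 | 0.06 | 0.02 |
| 4 h | 2 | 20-67% | 0.14 | 0.07 | 0.03 |
| 4 h | 5 | 38-83% | 0.13 | 0.07 | 0.02 |
| 4 h | 10 | 56-91% | 0.10 | 0.05 | 0.01 |

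Under these assumptions, sampling time alone gives an SD of 0.10-0.25 if unrestricted, 0.05-0.14 over a 2-8 h spread, and 0.01-0.05 in a 2-hour window.

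**Step 4: the baseline rows side by side.** Section 14.1.1 and calendar 13.2 put the baseline biopsy in screening. Calendar 13.1 puts it at C1D1, with no pre-dose label. Both cannot be followed. Section 5.3.1 makes the biopsy mandatory in the first 10 Stage I patients, whom it describes as among the first 18 enrolled. Section 5.1 starts Stage I after the six-patient lead-in. How many of the 10 would follow calendar 13.1 is therefore unsettled: up to 6 if lead-in patients count, none if they do not.

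**Step 5: bloods.** No section assigns pSTAT3 to blood. For immune cells, section 4.5 reports that neutrophil falls after dosing reversed within 12-24 h off drug, so at least one blood count follows dosing on a scale of hours. Nothing comparable is said of ctDNA.

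**The case against.** **The effect size is assumed.** This stands. The half-life comes from plasma in healthy volunteers, tumor pSTAT3 recovery is unknown, and peak-to-trough is the extreme comparison. Daytime biopsies would probably spread less. A reader might infer that timing noise is as large as the drug effect, but the documents do not support that.

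**The C1D1 mark is only a calendar slip.** Largely accepted. A reader might infer that lead-in baselines are taken after dosing and understate the change. Section 14.1.1 says prior to treatment, sections 6.1 and 12.2.4 also call the biopsy pre-treatment, and section 12.1 runs screening up to the first-dose day. The rows conflict, but a dosed baseline is not shown.

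**Dose times are already recorded.** Correct. The Appendix D diary has clock times for both daily doses and is reviewed at each visit (11.5). The protocol does not ask for the matching collection time. The laboratory manual, not among the documents, might ask for it, but it is cited only for processing and shipping.

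**Samples will not fall in a treatment hold.** Mostly right. Section 9.1 makes starting a cycle conditional on Day 1 criteria, so failing them defers the cycle. A hold that begins during C2D1-C2D8 remains possible.

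**Other readings go too far.** No section treats end-of-treatment blood as on-treatment. The earlier frozen tissue allowed by 5.3.1 must have had no intervening therapy, so dose timing does not bear on it.

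**A narrow window could lose pairs.** A fair point for CT-guided biopsies at three sites. Peak and trough also answer different questions: maximal or sustained inhibition. This argues against imposing a particular window, but not against choosing one and recording the time.

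**Conclusion.** The point holds in limited form. The second biopsy is tied to days only, and the stated half-life and dosing interval imply roughly an 8- to 64-fold range of plasma concentration across the permitted times. This part rests on first-order decay and the protocol's own figures. The effect on pSTAT3 could be material (SD 0.10-0.25 on the inhibition scale with unrestricted timing), but that part rests on assumed peak/IC50 ratios and on tumor pSTAT3 following plasma concentration without delay.

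The 13.1 biopsy row conflicts with 13.2 and 14.1.1 and must be reconciled. The pharmacokinetic wording in 17.2 has no scheduled data behind it. The bloods raise a narrower concern, for immune-cell populations only.

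The consequence is confined to a secondary and an exploratory objective in about 10 pairs, for which 17.2 already limits the biomarker analysis to exploratory use. The primary response rate and the two-stage decision are untouched. The change should be made because it is cheap and because a collection time not recorded may not be recoverable.

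**What to change.** 1. In 13.1, move the baseline biopsy mark from C1D1 to Screening to match 13.2 and 14.1.1. In both calendars, label C1D1 research blood as pre-dose.
2. In 13.1, 13.2 and 14.1, set one sampling window relative to that day's dose for the Cycle 2 biopsy and the on-treatment immune-cell bloods. The sponsor should choose peak or trough and state the reason. Apply it where feasible, and exclude no pair for missing it.
3. Record the clock time of each collection and link it to the dose time in the Appendix D diary. In 17.2, report or adjust for time since last dose, and state whether drug was held at sampling.
4. Delete *Pharmacokinetic* from 17.2, since no concentration sample is scheduled.

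The cost is calendar and wording edits, one collection-time field, and some coordination of biopsy appointments with dosing. No extra sample or procedure is needed.

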14.1.2 Blood samples

Whole blood will be requested as outlined in section 13.2 for peripheral blood mononuclear cell (PBMC) and circulating tumor DNA (ctDNA) collection to evaluate the effect of ruxolitinib on circulating immune cell populations before and during treatment and to further evaluate ctDNA as a potential biomarker of disease response.

See laboratory manual for detailed processing and shipping instructions for all correlative study specimens.

Shipping Instructions:

Shipments will be sent to the [name] laboratory by batch shipments when possible.

[name] Laboratory
[name]
[name]
[name]

The analyzing laboratories should be notified by email (Study listserv email: [contact]) the day the samples are sent. The email will contain the following information:

- Subject ID number
- Subject Initials
- Date of collection
- Time point (e.g. baseline, Cycle 2 Day 1, end of treatment, etc)
- Name of study center
- Shipment date
- Contents of shipment

All samples should be directed to the address listed above. Samples should be shipped via courier so that the package is tracked appropriately (specifically Federal Express or UPS). The samples should be shipped for morning delivery, Monday through Thursday for optimal processing.

Samples will be tracked through a Microsoft Excel tracker.

15. MEASUREMENT OF EFFECT

15.1 Antitumor Effect – Solid Tumors

For the purposes of this study, patients should be re-evaluated for response every 8 weeks weeks. In addition to a baseline scan, confirmatory scans should also be obtained 4 of weeks weeks following initial documentation of objective response.

Response and progression will be evaluated in this study using the international criteria proposed by the revised Response Evaluation Criteria in Solid Tumors (RECIST) guideline (version 1.1) [Eur J Ca 45:228-247, 2009]. Changes in the largest diameter (unidimensional measurement) of the tumor lesions and the shortest diameter in the case of malignant lymph nodes are used in the RECIST criteria.

15.2 Definitions

Evaluable for toxicity: All patients will be evaluable for toxicity from the time of their first treatment with ruxolitinib.

Evaluable for objective response: Only those patients who have measurable disease present at baseline, have received at least one cycle of therapy, and have had their disease re-evaluated will be considered evaluable for response. These patients will have their response classified according to the definitions stated below. (Note: Patients who exhibit objective disease progression prior to the end of cycle 1 will also be considered evaluable.)

Evaluable Non-Target Disease Response: Patients who have lesions present at baseline that are evaluable but do not meet the definitions of measurable disease, have received at least one cycle of therapy, and have had their disease re-evaluated will be considered evaluable for non-target disease. The response assessment is based on the presence, absence, or unequivocal progression of the lesions.

15.3 Disease Parameters

Measurable disease: Measurable lesions are defined as those that can be accurately measured in at least one dimension (longest diameter to be recorded for non-nodal lesions and short axis for nodal lesions) as ≥ 20 mm by chest x-ray, as ≥ 10 mm with CT scan or MRI, or ≥ 10 mm with

calipers by clinical exam. All tumor measurements must be recorded in millimeters (or decimal fractions of centimeters).

Note: Tumor lesions that are situated in a previously irradiated area might or might not be considered measurable. If the investigator thinks it appropriate to include them, the conditions under which such lesions should be considered must be defined in the protocol.

Malignant lymph nodes: To be considered pathologically enlarged and measurable, a lymph node must be ≥ 15 mm in short axis when assessed by CT scan or MRI (CT scan slice thickness recommended to be no greater than 5 mm). At baseline and in follow-up, only the short axis will be measured and followed.

Non-measurable disease: All other lesions (or sites of disease), including small lesions (longest diameter < 10 mm or pathological lymph nodes with ≥ 10 to < 15 mm short axis), are considered non-measurable disease. Bone lesions, leptomeningeal disease, ascites, pleural/pericardial effusions, lymphangitis cutis/pulmonitis, inflammatory breast disease, and abdominal masses (not followed by CT or MRI), are considered as non-measurable.

Note: Cystic lesions that meet the criteria for radiographically defined simple cysts should not be considered as malignant lesions (neither measurable nor non-measurable) since they are, by definition, simple cysts. Cystic lesions thought to represent cystic metastases can be considered as measurable lesions, if they meet the definition of measurability described above. However, if non-cystic lesions are present in the same patient, these are preferred for selection as target lesions.

Target lesions: All measurable lesions up to a maximum of 2 lesions per organ and 5 lesions in total, representative of all involved organs, should be identified as target lesions and recorded and measured at baseline. Target lesions should be selected on the basis of their size (lesions with the longest diameter), be representative of all involved organs, but in addition should be those that lend themselves to reproducible repeated measurements. It may be the case that, on occasion, the largest lesion does not lend itself to reproducible measurement in which circumstance the next largest lesion which can be measured reproducibly should be selected. A sum of the diameters (longest for non-nodal lesions, short axis for nodal lesions) for all target lesions will be calculated and reported as the baseline sum diameters. If lymph nodes are to be included in the sum, then only the short axis is added into the sum. The baseline sum diameters will be used as reference to further characterize any objective tumor regression in the measurable dimension of the disease.

Non-target lesions: All other lesions (or sites of disease) including any measurable lesions over and above the 5 target lesions should be identified as non-target lesions and should also be recorded at baseline. Measurements of these lesions are not required, but the presence, absence, or in rare cases unequivocal progression of each should be noted throughout follow-up.

